5.1.3 Enrolment

After signing the informed consent, if an individual is determined to be eligible for study participation, the investigator will enroll the subject and enter the subject information into randomization system, Source Data Base for Internet Randomization (SBIR).

5.1.4 Randomization

5.1.4.1 Randomization of supplies

The randomization of supplies within blocks will be performed at GSK, using MATerial EXcellence (MATEX), a program developed for use in Statistical Analysis System (SAS®) (Cary, NC, USA) by GSK. Entire blocks will be shipped to the study centre.

5.1.4.2 Study group and treatment number allocation

Enrolled subjects will be randomized in the SBIR system to one of two different blood draw schedules according to a 1:1 ratio, described as follows:

- Subjects getting blood draws at Day 1, Day 4 and Day 29.
- Subjects getting blood draws at Day 1, Day 6 and Day 29.

Allocation of the subject to a blood draw schedules at the investigator site will be performed using a central randomization system on internet (SBIR).

The randomization algorithm will use 3 minimization procedure accounting for the previous vaccination status (Menveo, Menactra or Vaccine-Nai've study group).

For each dose, the study staff in charge of vaccine administration will access SBIR, provide the subject ID, and the system will provide a treatment number consistent with the allocated treatment arms.

SBIR will also be used to ensure adequate and appropriate distribution of enrolment of naïve subjects across all sites.

For any question regarding SBIR, please refer to the SBIR user guide and SBIR Manual for specific instructions. If for any reason, after signing the informed consent form (ICF), the subject who is eligible and enrolled fails to be randomized, this is called a randomization failure and the early termination study procedures must be applied. The reason for all randomization failures should be recorded in the Screening and Enrolment Log and in the source document as specified in the Source Documentation Agreement Form (SDAF). The information on subjects who are randomization failures should be

kept distinct from subjects who are screen failures, as described in [section S.1.2, Screening](#).

If for any reason, after enrolment the subject fails to undergo treatment/study procedures this is an Early Termination and the reason should be recorded in source document as specified in the Source Documentation Agreement (SD.AF). The information on these Early Termination subjects should be kept distinct in the source documentation from subjects who are screen failures, as described in [section 5.1.2, Screening](#).

5.2 Vaccination Clinic Visit

The first vaccination will be performed on Day 1.

For studies which have visits for concomitant vaccinations or treatments, see [section 6.5, Prior and Concomitant Medications and Vaccines](#) for those visit procedures.

Ensure **all** blood samples are taken **p1i or** to the vaccination .

After completing the pre-vaccination procedures on day 1, administer the vaccine to the subject according to the procedures described in [section 6.3, Vaccine Preparation and Administration](#). Observe the blinding procedures described in [section 3.3, Blinding Procedures](#).

Prior to administration of study vaccination, confirm that the subject does not meet any criteria for delaying additional study vaccinations as described in [section 4, Selection of Study Population](#).

5.2.1 Post-vaccination Procedures

The following post-vaccination procedures will be performed on day 1.

- After vaccination, the subject will be observed for at least 30 minutes including observation for unsolicited adverse events, solicited adverse events, and body temperature measurement. Record **all** safety data collected during this time in the subject's source document.
- A Subject Diary will be used in this study to document solicited adverse events. The Subject Diary is the only source for collection of these data; therefore, it is critical that the subject completes the Subject Diary correctly. The subject should be trained on how and when to complete each field of the Subject Diary.
- The subject and/or parent(s)/legal guardian(s) should be trained on how to self-measure local solicited adverse events. The measurement of solicited local adverse events is to be performed using the ruler provided by the site.

- The subject and/or parent(s)/legal guardian(s) should be instructed how to perform body temperature measurement using the thermometer provided by the site. If the subject feels unusually hot or cold during the day, the subject and/or parent(s)/legal guardian(s) should check body temperature. If the subject has fever, the highest body temperature observed that day should be recorded in the Subject Diary.

Subject Diary training should be directed at the individual(s) who will perform the measurements of adverse events and who will enter the information into the Subject Diary. This individual may not be the subject and/or parent(s)/legal guardian(s), but if a person other than the subject and/or parent(s)/legal guardian(s) enters information into the Subject Diary, this person's identity must be documented in the Subject Diary or subject's source record. Any individual that makes entries into the Subject Diary must receive training on completion of the Subject Diary at the time of the visit. This training must be documented in the subject's source record.

The same individual should complete the Subject Diary throughout the course of the study.

- The site should schedule the next study activity clinic visit on Day 4 or Day 6 depending to which blood draw schedule subject was randomized to with the subject and/or parent(s)/legal guardian(s).

The subject and/or parent(s)/legal guardian(s) will be reminded to complete the Subject Diary and to contact the site if there are any questions, and to contact the site immediately (or as soon as the subject is medically stable) if the subject has a medical condition that leads to a hospitalization or an emergency room visit or to a visit to/by a doctor or is of concern.

5.2.2 Post-vaccination Reminders

Reminder calls or alerts are not intended to be an interview for collection of safety data. If the subject and/or parent(s)/legal guardian(s) wishes to describe safety information, this information should only be collected by a healthcare professional at the site, and the safety data described must be written down in the subject's medical chart.

Subject Diary Reminder Calls

Subject Diary reminder calls will be performed on day 3 and day 5. The purpose of this call is to remind the subject and/or parent(s)/legal guardian(s) about completion of the Subject Diary. The call follows the Subject Diary Reminder Telephone Call Script provided to the site. The subject and/or parent(s)/legal guardian(s) should be reminded to contact the site via the telephone number provided in the informed consent to discuss

medical questions. If the clinic visit at Day 4 or Day 6 overlaps with the specified window of the Day 3 or Day 5 reminder call, the Day 3/Day 5 reminder call may be omitted.

5.3 Post-vaccination Visit(s)

Post-vaccination visits will be performed on Day 4 or Day 6 according to the blood draw schedule to which subject was randomized and Day 29.

5.3.1 Follow-up Clinic Visit(s)

Follow-up clinic visits will be performed on Day 4 or Day 6 according to the blood draw schedule to which subject was randomized and on Day 29. During the follow-up clinic visit:

- Subject Diary will be reviewed at Day 29. No changes to the information recorded within the Subject Diary are permissible. For details on the Subject Diary see [sections 3.4.2, Tools Used for Data Collection](#) and [5.2.1, Post-vaccination Procedures](#). The subject and/or parent(s)/legal guardian(s) will be interviewed to determine if any unsolicited adverse events occurred and if any concomitant medications or vaccines were taken/received in the time since the last clinic visit. This interview will follow a script which will facilitate the collection of relevant safety information. The healthcare professional reviewing these data will discuss the symptoms (if any) reported by the subject and will determine if any additional diagnoses and/or adverse events are present. Adverse events reported by the subject and/or parent(s)/legal guardian(s) at this follow-up clinic visit must be recorded in the subject's source document and on an Adverse Events CRF, as specified in [section 7.1, Safety Assessment](#), and not written on the script used for the interview.
- Perform a brief symptom-directed physical examination if necessary according to symptoms the subject has reported. This is a physical examination that will include an examination of organ systems that are relevant to the investigator based on review of the subject's reported adverse events and concomitant medication use. This assessment may include: measurement of vital signs, body temperature and a check of general appearance. The physical assessment must be performed by the investigator or designee of the investigator, who is qualified to perform a physical assessment in accordance with their institutional policy. Corresponding information is documented in the subject's source document and CRF(s).
- Collect a blood sample (see [section 3.5, Collection of Clinical Specimens](#) for additional information).

The site should schedule the next study activity safety call with the subject and/or parent(s)/legal guardian(s).

The subject and/or parent(s)/legal guardian(s) will receive a written reminder of the next planned study activity. The subject and/or parent(s)/legal guardian(s) will be reminded to contact the site if there are any questions and to contact the site immediately (or as soon as the subject is medically stable) if the subject has a medical condition that leads to a hospitalization or an emergency room visit.

5.3.2 Safety Follow-up Calls

Safety follow-up call will be performed on Day 15, Day 91 and Day 181.

Safety follow-up calls are calls made to the subject by a healthcare professional designated on the site log. These calls will follow a script which will facilitate the collection of relevant safety information. The subject and/or parent(s)/legal guardian(s) will be interviewed according to the script, and information related to unsolicited adverse events (only at Day 15), serious adverse events (SAEs), medically attended adverse events, AEs leading to withdrawal and concomitant medications or vaccinations associated with those events will be reviewed. All safety information described by the subject must be written down in a designated location within the source document and not written on the script used for the telephone call.

The site should schedule the next study activity with the subject and/or parent(s)/legal guardian(s).

The subject and/or parent(s)/legal guardian(s) will be reminded to contact the site if there are any questions and to contact the site immediately (or as soon as the subject is medically stable) if the subject has a medical condition that leads to a hospitalization or an emergency room visit.

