Medically-attended AEs, AEs leading to study withdrawal and SAEs will be collected during the entire study period. These data will be captured by interviewing the subject and/or subjects' parents / guardian (as applicable) during the site visits and phone calls and by review of available medical records. Subjects and/or parents / guardian will be encouraged to call the site in the event of any medically-attended AEs or any AEs which they perceive as being of concern during the entire study period.

Table 2: Schematic diagram of the V59_77 study design.

Day 1	Day 4	Day 6	Day 15	Day 29	Day 91	Day 181
Blood draw (all subjects) Menveo	Blood draw (50% of subjects)	Blood draw (50% of subjects)	Safety Phone call	Blood draw (all subjects)	Safety Phone call	Safety Phone call Study termination

Number of Subjects planned: Approximately 700 subjects are planned for enrolment

Name of Sponsor:	Protocol number:	Generic name of study vaccine(s):
GlaxoSmithKline Biologics S.A	V59_77	Meningococcal (groups A, C, W, and Y) oligosaccharide diphtheria CRM-197 conjugate vaccine
into this study, approximately 300 subjects who previously received Menveo (Menveo-Menveo group), 300 subjects who previously received Menactra (Menactra-Menveo group) and 100 meningococcal vaccine-naive subjects (Naive group). Assuming a 10% drop-out rate that should provide approximately 630 evaluable subjects.		
Study Population and Subject Characteristics: The list of inclusion and exclusion criteria is included in protocol section 4, Selection of Study Population .		
Study Procedures: The study includes three clinic visits, one vaccination, three blood draws, and three safety phone calls for each subject. All study procedures associated with the pre-vaccination, vaccination, post-vaccination and study termination visit are described in section 5.0 .		
Study Vaccines: GlaxoSmithKline Meningococcal MenAC\1VY- CRM191 vaccine (Menveo): Meningococcal (groups A, C, W and Y) oligosaccharide diphtheria CRM-197 conjugate vaccine is supplied as a vial that contains 10 µg of serogroup A oligosaccharides and 5 µg of serogroups C, W and Y oligosaccharides, conjugated to Corynebacterium diphtheriae CRM191 protein. Overall injection volume of 0.5 mL. The vaccine will be administered intramuscularly, preferably in the deltoid area of the non-dominant arm.		
Primary Endpoint(s): Immunogenicity Endpoints: The following measures will be summarized for Menveo-Menveo and Menactra-		

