Reminder Phone calls: Two (2) reminder phone calls will be conducted at Day 3 and Day 5 after the study vaccination to remind the subject/legal guardian to complete the diary card.

Safety phone calls: Three (3) safety phone calls (at Day 15, Day 91 and Day 181) will be conducted to collect any medically-attended AEs, AEs leading to withdrawal, SAEs, related medications and any vaccinations. In addition, all unsolicited AEs and related medications occurring after the vaccination will be collected during the safety call at Day 15. The Day 181 Safety Phonecall will also serve as the termination visit.

Solicited Adverse Events (injection site pain, erythema, induration, fatigue, headache, myalgia, arthralgia, loss of appetite, nausea, chills and fever) occurring on the day of vaccination and the following six days (Day 1 through Day 7) will be recorded daily using a Diary Card for all subjects.

Unsolicited AEs occurring within 28 days after study vaccination will be collected. Qualified site staff will interview the subject by phone approximately 14 days after vaccination and in person at the study site approximately 28 days after study vaccination to assess the occurrence of any unsolicited AEs.

Medically-attended AEs AEs leading to study withdrawal and SAEs will be collected during the entire study period. These data will be captured by interviewing the subject and/or subjects' parents/ guardian (as applicable) during the sitevisits and phone calls and by review of available medical records. Subjects and/or parents / guardian will be encouraged to call the site in the event of any medically-attended AEs or any AEs which they perceive as being of concern during the entire study period.

Table 3.1-2: Schematic diagram of the V59_77 study design

Day 1	Day 4	Day 6	Day 15	Day 29	Day 91	Day 181
Blood draw (all subjects Menveo	Blood draw (50% of subjects)	Blood draw (50% of subjects)	Safety Phone call	Blood draw (all subjects)	Safety Phone call	Safety Phone call Study termination

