7.1.2 Unsolicited Adverse Events

An unsolicited adverse event is an adverse event that was not solicited using a Subject Diary and that was spontaneously communicated by a subject and/or parent(s)/legal guardian(s) who has signed the informed consent.

Potential unsolicited AEs may be medically attended (defined as symptoms or illnesses requiring hospitalization, or emergency room visit, or visit to/by a health care provider,) or were of concern to the subject and/or parent(s)/legal guardian(s). In case of such events, subjects and/or parent(s)/legal guardian(s) will be instructed to contact the site as soon as possible to report the event(s). The detailed information about the reported unsolicited AEs will be collected by the qualified site personnel during the interview and will be documented in the subject's records.

Unsolicited AEs that are not medically attended nor perceived as a concern by subjects and/or parent(s)/legal guardian(s) will be collected during interview with the subject [and/or parent(s)/legal guardian(s) and by review of available medical records at the next visit (see [section 5.3, Post-vaccination Visit\(s\)](#)).

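### Reminders after Day 1 leave out doctor visits and events of concern, so medically attended AEs after Day 29 rely mainly on interviews nominally 62 and 90 days apart, plus available records

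*Protocol*

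**What the plan says.** The broad statement appears in three places. Protocol 3.1 says subjects, and parents or guardians, are "encouraged to call the site in the event of any medically-attended AEs or any AEs which" worry them, at any time in the study. The synopsis and SAP section 2 carry the same sentence. Just before it, each names the means of capture: interviews at visits and calls, and review of available medical records.

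Protocol 7.1.2 describes medically attended events as those "requiring hospitalization, or emergency room visit, or visit to/by a health care provider". It says subjects will be instructed to contact the site as soon as possible about such events or events of concern, but names no period.

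The reminders in Protocol section 5 are not uniform. On Day 1 (5.2.1) the subject is to contact the site for a condition that "leads to a hospitalization or an emergency room visit or to a visit to/by a doctor or is of concern". At the Day 4/6 and Day 29 clinic visits (5.3.1) the trigger is "if the subject has a medical condition that leads to a hospitalization or an emergency room visit". The safety calls (5.3.2) use the same shorter form: contact is asked for only when someone "has a medical condition that leads to a hospitalization or an emergency room visit".

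Active collection does continue. At the safety calls, "serious adverse events (SAEs), medically attended adverse events, AEs leading to withdrawal and concomitant medications or vaccinations associated with those events will be reviewed".

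**The concern.** Under Protocol 7.1.3, any AE leading to a visit to a healthcare provider is medically attended. An ordinary doctor visit therefore counts towards secondary safety endpoint 5 in 8.1.2.1, which runs from Day 1 through Day 181. The reminders from Day 4/6 onwards name only the two most serious kinds of attendance. A subject hears the full rule once, on Day 1, and the shorter one at Day 4/6, Day 15, Day 29 and Day 91, four times before the final call.

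The protocol gives no reason for the narrowing. The later sentences repeat the 5.2.1 sentence without its last two limbs, which looks more like an omission than a decision.

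At stake are the completeness and timeliness of medically attended AE reporting in the second part of follow-up. Timeliness has a further side: the SAE definition in 7.1.4 includes important medical events that need not involve hospitalization, and the 24-hour reporting clock in 7.1.5 starts when the site becomes aware.

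**Working it through.** The plan states no figure on this point. The check is a comparison of passages plus arithmetic on the visit schedule.

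**Triggers for contacting the site**

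| Place | When it applies | Hospital or ER | Doctor visit | Of concern |
|---|---|---|---|---|
| Synopsis, Protocol 3.1, SAP 2 | entire study | yes | yes | yes |
| Protocol 7.1.2 | no period given | yes | yes | yes |
| Protocol 5.2.1 | Day 1 | yes | yes | yes |
| Protocol 5.3.1 | Day 4/6, Day 29 | yes | no | no |
| Protocol 5.3.2 | Day 15, 91, 181 | yes | no | no |

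For the first row, doctor visits follow from the definition of medically attended in 7.1.2 and 7.1.3.

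**Time between scheduled contacts**

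Inputs (Protocol Time and Events Table; SAP Table 2-2): Day 4 or 6 (-1/+1), Day 15 (-2/+2), Day 29 (-7/+14), Day 91 (-14/+14), Day 181 (-14/+14).

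Nominal gap = next day - previous day. Longest allowed gap = (next day + upper window) - (previous day + lower window, a negative number).

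| Interval | Nominal | Longest allowed |
|---|---|---|
| Day 4 to 15 | 15 - 4 = 11 | 17 - 3 = 14 |
| Day 6 to 15 | 15 - 6 = 9 | 17 - 5 = 12 |
| Day 15 to 29 | 29 - 15 = 14 | 43 - 13 = 30 |
| Day 29 to 91 | 91 - 29 = 62 | 105 - 22 = 83 |
| Day 91 to 181 | 181 - 91 = 90 | 195 - 77 = 118 |

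Nominal gaps are at most 14 days up to Day 29, so the wording of the early reminders matters little. The reminders that precede the long gaps are those at Day 29 (5.3.1) and Day 91 (5.3.2). The Day 181 call is the termination contact (5.5), so its reminder has almost no bearing on the endpoint.

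**Size of any loss.** This would need the true rate of medically attended AEs after Day 29, the share missed under the present wording, and the share still missed under the fuller wording. The documents give none of these. The endpoint is also counted per subject, so a forgotten later visit changes nothing for a subject who already has a recorded event. No estimate is offered.

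**The case against.** The strongest reply is that capture does not depend on these reminders. The Time and Events Table schedules assessment of medically attended AEs at the visits and calls. Protocol 5.3.2 and 5.5 make the calls scripted interviews that cover them explicitly, and available medical records are a second source. Calls initiated by the subject supplement this. That stands: the risk is late or incomplete capture, not absence of collection.

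A reader might infer that the later reminders replace the Day 1 instruction. The documents do not support that. Nothing in 5.3.1 or 5.3.2 revokes 5.2.1, 7.1.2 or the study-long encouragement; the broader message is simply not repeated. A reader might also infer that doctor visits after Day 4/6 rest on recall alone. That leaves out the review of available records.

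Two smaller replies also stand. The limb on events of concern adds little to the endpoint after Day 29: a later event that is not medically attended, not serious and does not lead to withdrawal falls outside endpoint 5. And the call scripts are not among the documents, so they may already mention doctor visits.

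These replies narrow the consequence. They do not remove the mismatch between 5.3.1 and 5.3.2 and the other passages.

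**Conclusion.** The inconsistency holds and the passages should be reconciled. The reminders in 5.3.1 and 5.3.2 are narrower than the synopsis, 3.1, 5.2.1, 7.1.2 and SAP section 2. Prompt reporting of ordinary doctor visits is therefore not reinforced after Day 1. After Day 29, their capture relies mainly on two interviews, with nominal gaps of 62 and 90 days (83 and 118 at the edges of the windows), plus whatever records are available.

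It is tempting to state a downward bias in the Day 1 to 181 percentage as so many points or standard errors. That would rest on invented event rates and miss rates, and would charge to the wording a loss of recall that might occur anyway. The documents support a risk, not a size.

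The consequence is limited. Safety has no success criteria (Protocol 8.2.2.1), no hypotheses (8.4.3.1.4) and no statistical comparison between groups (8.4.3.1.6), and the reminders are the same in every group. Only descriptive percentages are affected. This is a cheap improvement, not a flaw that threatens a conclusion. It assumes that sites take their wording from section 5 and that the unseen call scripts follow it.

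**What to change.** In Protocol 5.3.1 and 5.3.2, extend the reminder to match 5.2.1, so that it covers a condition that "leads to a hospitalization or an emergency room visit or to a visit to/by a doctor or is of concern". Check the safety call scripts, especially the Day 91 script, and align them. The change matters most at Day 29 and Day 91, before the two long gaps. The written reminder in 5.3.1 concerns the next planned study activity, so it need not change unless the sponsor wants the same sentence there.

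The cost is one phrase in two sections and a check of the scripts. The downside is a few more unscheduled calls to sites. No visit, procedure or analysis changes.

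If the narrower trigger was intended, the protocol should say so and the synopsis, 3.1, 7.1.2 and SAP section 2 should be brought into line with it.
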